6.5. Statistical Tests

The default significant level will be (5%), CIs will be 95% and all tests will be two-sided, unless otherwise specified in the description of the analyses.

95% CI for proportion will be based on exact Clopper-Pearson CI [18].

95% CI for group difference in proportion will be based on Miettinen and Nurminen CI [18].

The group adjusted GMT ratio will be based on a back transformation of group contrast in an ANCOVA model applied to the logarithm-transformed titers.

6.6. Common Calculations

GMT/GMC:

Prior to any statistical analysis that assumes normally distributed observations, antibody concentrations or titers will be log10-transformed. GMT/GMC calculations are performed by taking the inverse logarithm of the mean of the log titer or concentration transformations.

The GMT/GMC will be calculated using the following formula:

$$10^{\frac{\sum_{i=1}^n \log_{10} (t_i)}{n}}$$

where t_i = concentrations or titers for each antibody, n = number of antibodies examined. Non-quantifiable antibody titers or concentrations will be converted as described in [Table G](#) for the purpose of GMT/GMC calculation. Cut-off values are defined by the laboratory before the analysis.

MGI is defined as the geometric mean of the within participants ratios of the post-dose titer (at 1 month after the RSVPreF3 OA investigational vaccine dose [Day 31 for Co-Ad group, Day 61 for Control group]) over the pre-dose titer (at pre-vaccination [Day 1 for Co-Ad group and Day 31 for Control group]).

Geometric mean fold rise (GMFR) in serotype-specific OPA titers for PCV is the within participant ratio of OPA GMT at 1 month post PCV vaccination (Day 31 for Co-Ad group and Control group) over pre vaccination (Day 1 for Co-Ad group and Control group).

4-fold rise is defined as a post-vaccination titer \geq 4 times the LLOQ for that measure (PCV, RSV-A, RSV-B).

Table G: Assay Derivation Rules

IS.ISORRES	Derived value
“NEG”, “-”, or “(-)”	assay cut-off/2
“POS”, “+”, or “(+)”	assay cut-off
“< value” and value is \leq assay cut-off	assay cut-off/2
“< value” and value is $>$ assay cut-off	Value
“> value” and value is $<$ assay cut-off	assay cut-off/2
“> value” and value is \geq assay cut-off	Value
“value” and value is $<$ assay cut-off	assay cut-off/2
“value” and value is \geq assay cut-off	Value
“value” and value is $>$ ULOQ	ULOQ
All other cases	missing

Note: The Reverse Cumulative Distribution curves (RCC) generated will not use the ULOQ values but the exact value if the exact value is greater than ULOQ.

Numerical serology results will be derived from the content of IS.ISORRES in the SDTM dataset. For all the assays available for the study, assay derivation rules are included in Table G.

LLOQ and ULOQ values for PCV OP Ab titers and for RSV-A and RSV-B titers and concentrations are as per APPENDIX 3 of this SAP.

6.7. Software Version

All analyses will be conducted using SAS version 9.4 or above.

7. STATISTICAL CONSIDERATIONS

7.1. Adjustments for Covariates and Factors to be Included in Analyses

The following factors will be used in the ANCOVA analyses: age group at vaccination (60 to 69, 70 to 79 or \geq 80 YOA) and study intervention group (Co-Ad or Control). The following covariate will be used in the ANCOVA: pre-dose \log_{10} -transformed titer as covariate. For details, refer to 15.1 and 15.2.

7.2. Multicenter Studies

This study will be conducted by multiple investigators in multiple countries. The participants will be randomized to one of the 2 groups (refer to Table A in section 3.1) which will be performed in a 1:1 ratio prior to intervention to provide approximately 545 enrolled participants per study intervention group.

7.3. Missing Data

Missing data (missing, incomplete or partial dates, AE measurement, prior and concomitant medications and death date) will be handled as per [APPENDIX 2](#) of this SAP.

Missing immunogenicity data will not be imputed. Titers below assay cut-off (i.e., lower limit of quantification or < LLOQ) will be replaced by half the assay cut-off (LLOQ/2) and titers above the assay cut-off (i.e., upper limit of quantification or > ULOQ) will be replaced by the ULOQ for the purpose of GMC/GMT computation.

7.4. Multiple Comparisons / Multiplicity

There are 3 primary endpoints to be accounted for in this study. In order to eliminate the need to adjust alpha, testing for these endpoints will take the following sequence:

- 1st Sequence:
 - 1) The upper limit (UL) of the 2-sided 95% CI of the GMT ratio (control group divided by Co-Ad group) for each individual pneumococcal vaccine serotype as measured by OP Ab is ≤ 2 .
AND
 - 2) The UL of the 2 sided 95% CI of the GMT ratio (control group divided by Co-Ad group) between the control group versus Co-Ad group for RSV-A neutralizing antibody titer one month after the RSVPreF3 OA investigational vaccine dose is ≤ 1.5 .
- 2nd Sequence:
 - 3) The UL of the 2 sided 95% CI of the GMT ratio (control group divided by Co-Ad group) between the control group versus Co-Ad group for RSV-B neutralizing antibody titer one month after the RSVPreF3 OA investigational vaccine dose is ≤ 1.5 .

Testing will progress in the 2nd sequence only if the 1st sequence is a success.

7.5. Examination of Subgroups

Subgroup analyses by age category (60-69, 70-79, ≥ 60 , ≥ 65 , ≥ 80 YOA) will be performed for secondary immunogenicity endpoints, solicited events, unsolicited events, serious AEs and pIMD summaries.

8. OUTPUT PRESENTATIONS

[APPENDIX 1](#) shows conventions for presentation of data in outputs.

The templates provided with this SAP describe the presentations for this study and therefore the format and content of the summary tables, figures, and listings to be provided by IQVIA Biostatistics. Statistical output numbering will follow 'ICH E3 Structure and Content of Clinical Study Reports'.

9. DISPOSITION AND WITHDRAWALS

All participants who are enrolled in the study (those who received a study intervention, had a blood draw before study intervention administration, or were randomized), i.e., those accounted for in the ENR, will be accounted for in this study.

9.1. Disposition

Participant disposition, withdrawals, and reasons for exclusion from each analysis set, including inclusion as well as exclusion criteria will be presented for the ENR. Participant disposition will be summarized for screen failures from SCR to ENR. Specifically, the number of participants, vaccinated, completed the study, discontinued from the study and the reason for discontinuation will be summarized by study intervention for the ENR. Additionally, the number of participants returning for each visit for the ES will be presented.

A listing of the disposition for all participants with early withdrawal or discontinuation will be provided.

9.2. Protocol Deviations

Protocol deviations (PDs) will be collected in a PD log, as detailed in the PDMP. All PDs will be assessed as either important or non-important. PDs will be reviewed by the sponsor, and their status confirmed by the time that all data

are cleaned for the EOS Analyses. A summary table presenting the number and percentage of participants with important PDs (i.e., those PDs associated to elimination from PPS) and the number and percentage of participants excluded from the PPS analyses will be presented for participants in the ES by study intervention. A listing of all PDs including an indicator of those excluded from the PPS will be provided.

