9.4 Interim Analysis

9.4.1 Sequence of Analysis

The analyses will be performed stepwise:

- A first analysis will be performed on all immunogenicity, reactogenicity and safety data available and as clean as possible, when data for at least primary and secondary endpoints up to Visit 2 (Day 31) (co-ad group) or Visit 3 (Day 61) (control group) are available for all participants. This analysis will be considered as final for those endpoints.
- An End of Study analysis will include all data obtained until 6 months post-last dose.

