4.1. Interim Analysis

There will be no interim analyses for this study.

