4.2. First Analysis

A First Analysis will be performed on all immunogenicity, reactogenicity and safety data available and as clean as possible, when data for at least primary and secondary endpoints up to Visit 2 (Day 31) (Co-Ad group) or Visit 3 (Day 61) (Control group) are available for all participants. This analysis will be considered as final for those endpoints.

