4.3. EOS Analysis

An End of Study analysis will include all data obtained until 6 months post-last dose.

If for any reason the First Analysis could not be performed prior to the EOS Analysis, then the First Analysis will be performed at EOS analysis.

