5. ANALYSIS SETS

Agreement and authorization of participants included / excluded from each analysis set will be conducted prior to

production for the interim analysis.

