APPENDIX 1. PROGRAMMING CONVENTIONS FOR OUTPUTS

IQVIA Output Conventions

Outputs will be presented according to the following:

Document Headers

All TFL is to include the following header:

Vaccine: RSVPreF3 OA (RSV OA=ADJ-019)

Study 219276 – DELIVERY DESIGNATION

where delivery designation is the name of the current delivery, e.g., DRY RUN, INTERIM ANALYSIS, FINAL ANALYSIS, etc.

Dates & Times

Depending on data available, dates and times will take the form yyyy-mm-ddThh:mm:ss.

Spelling Format

English US

Presentation of Study Intervention Groups

For outputs, intervention groups will be represented as follows and in the given order:

Study Intervention Group	For Tables and Figures	For Listings (include if different to tables)
Co-Ad	Co-Ad	Co-Ad
Control	Control	Control

Presentation of Visits

For outputs, Co-Ad group visits will be represented as follows and in that order:

Long Name (default)	Short Name
Visit 1 (Day 1)	Day 1
Visit 2 (Day 31)	Day 31

For outputs, Control group visits will be represented as follows and in that order:

Long Name (default)	Short Name
Visit 1 (Day 1)	Day 1
Visit 2 (Day 31)	Day 31
Visit 3 (Day 61)	Day 61

Listings

All listings will be ordered by the following (unless otherwise indicated in the template):

- Randomized study intervention group (or intervention received if it's a safety output), first by Co-Ad group then Control group,
- Center-participant ID,
- Date (where applicable).

DECIMAL PLACES

Decimal places for categorical data

- For percentages one decimal will be displayed
- Differences in percentages and their corresponding confidence limits will be displayed with one more decimal than the maximum number used to display the individual percentages, for example the difference between two percentages displayed with one decimal will be displayed with two decimals.

Decimal places for Demographic and baseline characteristics will be as follows:

The mean, median, and SD for continuous baseline characteristics (age) will be presented with one decimal.

Serological Summary Statistics

The number of decimals used when displaying GMTs/GMCs and their CIs is shown in the following table:

GMT/GMC value	Number of decimals
<0.1	3
≥0.1 and <10	2
≥10 and <1000	1
≥1000	0

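### Could deviations that decide the per-protocol set be confirmed only after the First Analysis, which is final for the primary endpoints?

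*SAP*

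**What the plan says.** Protocol 9.3.1 and SAP 15 base the confirmatory non-inferiority analyses on the PPS. SAP 4.2 runs the First Analysis once primary and secondary endpoint data are in for everyone up to Visit 2 (Co-Ad) or Visit 3 (Control), and states: "This analysis will be considered as final for those endpoints". SAP 4.3 treats running it at EOS as a fallback: "If for any reason the First Analysis could not be performed prior to the EOS Analysis".

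Three sections of the SAP bear on when the PPS is settled:

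- Section 5 requires membership of each set to be agreed and authorized before "production for the interim analysis". Section 4.1, however, says: "There will be no interim analyses for this study".
- Section 5.1 calls for continuous monitoring of deviations, listings of excluded participants, a Data Review meeting and sponsor authorization, all before database lock. It does not say which lock. The final sets are derived after that lock.
- Section 9.2 says "PDs will be reviewed by the sponsor, and their status confirmed by the time that all data" "are cleaned for the EOS Analyses". It also identifies important deviations as those tied to removal from the PPS.

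The protocol describes the two-step sequence (a first analysis, then the EOS analysis) under the heading "9.4 Interim Analysis". SAP Appendix 1 keeps the term as an example of an output label: "where delivery designation is the name of the current delivery, e.g., DRY RUN, INTERIM ANALYSIS, FINAL ANALYSIS, etc".

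**The concern.** The three sections give three different deadlines, and none of them names the First Analysis. The one attached directly to deviations is the latest. A reader who takes 9.2 alone could conclude that the sponsor may still be deciding who leaves the PPS after the primary results by arm have been produced and declared final.

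That would matter here. The study is open-label, with only the testing laboratory blinded (protocol 6.3.5), and some exclusions involve judgment. Protocol 9.2.1 says that participants with certain conditions may be eliminated. Protocol section 8.0 leaves the PPS effect of an extended Visit 2 interval to individual decision. The first testing step needs all 20 serotypes and RSV-A to succeed before RSV-B is tested, so a change in membership that moved one borderline comparison could change the overall conclusion.

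**Working it through.** The plan gives no figure for this point, so the check is mainly a comparison of passages, with two small calculations.

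**1. What the interim analysis in SAP 5 refers to.** Protocol 9.4 carries that heading and describes exactly two analyses. The second is the EOS analysis. The first is therefore the only one to which the term can apply, and SAP 4.2 describes the same step as the First Analysis. On this reading SAP 5 already requires the sets to be authorized before the First Analysis, and the clash with SAP 4.1 is one of terminology.

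**2. Whether the deadlines can all be met together.**

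| SAP section | What is settled | Deadline |
|---|---|---|
| 5 | Membership of each analysis set | Before the interim analysis (the First Analysis, by step 1) |
| 5.1 | Data Review meeting, sponsor authorization | Before a lock that is not identified |
| 9.2 | Status of all deviations, important or not | EOS cleaning at the latest |

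Section 9.2 covers the whole log. That includes deviations arising between the last blood sample and the six-month contact, which cannot be confirmed before EOS cleaning. Its date is a latest date and does not require PPS-relevant deviations to wait. Confirming those before the First Analysis, and the rest by EOS, satisfies both 5 and 9.2.

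**3. Whether PPS membership depends on anything later.** SAP 5.5 counts elimination criteria up to the post-dose sample. For RSV that is Visit 2 (Co-Ad) or Visit 3 (Control). For PCV the bullet refers to the sample after RSV vaccination, while its own parenthesis says Visits 1 and 2. Either way the last relevant date is Visit 3 at the latest. SAP 4.2 waits for endpoint data to Visit 2 or Visit 3 from all participants, so every event that can remove someone has already occurred by then.

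**4. Time between last primary sample and EOS contact.** Inputs are protocol Tables 3 and 4, repeated as SAP Tables C and D. The contact is 180 to 210 days, and the last primary sample 30 to 42 days, after the same visit (Visit 1 for Co-Ad, Visit 2 for Control).

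- Minimum: 180 − 42 = 138 days
- Planned: 180 − 30 = 150 days
- Maximum: 210 − 30 = 180 days

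This is a gap per participant. The interval between the First Analysis and EOS cleaning also depends on enrollment, assay turnaround and cleaning time, which the documents do not give. Nor do they say how many deviations would be open.

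**5. The supporting analysis on the Exposed Set (ES).** SAP 15 requires it if 5% or more of vaccinated participants with serology are excluded from the PPS in any group. Assuming all 545 in a group have serology, 0.05 × 545 = 27.25. So 28 exclusions (28/545 = 5.14%) trigger it and 27 (27/545 = 4.95%) do not. The sample size allows for 545 − 490 = 55 non-evaluable participants per group, though those without serology would not count toward the trigger.

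**6. Whether a late deviation could change the result.** SAP 4.2 makes the First Analysis final for these endpoints, and no section provides for repeating the primary tests at EOS on a revised PPS.

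**The case for a change.** The best argument for amending the SAP is that step 1 is an inference. SAP 4.1 denies any interim analysis outright, and the SAP gives the First Analysis its own heading, so a literal reader may find that section 5 points at nothing. Section 5.1 does not fill the gap: if its lock is the EOS lock, the final sets would be derived after a final analysis. Section 9.2 links its deadline to the very deviations that remove participants from the PPS. In an open-label trial, judgments of this kind should be closed before results by arm exist, and a few words would say so. The ES analysis is conditional and only complements the PPS result.

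The observation about wording stands: three different deadlines are used, and none names the First Analysis. The claimed consequence does not. It requires 9.2 to override the more specific rules on set membership in 5 and 5.1, and nothing says that it does. Nor does the tension go away only if the First Analysis slips to EOS. It also goes away when PPS-relevant deviations are confirmed beforehand, which 9.2 permits and 5, on its natural reading, requires. Several PPS criteria are also objective: vaccine received, pre- and post-dose results present, blood-draw interval met. The SAP sends the detail of which deviations exclude to a deviations management plan, and it mentions a data review plan. Neither is available here, and either may set the timing.

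**Conclusion.** This is inconsistent terminology and no change to the plan follows. Followed as a whole, the plan gives a PPS authorized before a First Analysis whose results are then final, with EOS cleaning as the outer limit for the complete deviation log. Clearer wording would mainly record a sequence that the analysts would follow anyway.

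No effect on a GMT ratio, alpha, power or sample size is shown. The only sizes available are the 138 to 180 days between a participant's last primary sample and EOS contact, and the trigger of 28 exclusions in a group of 545 for the ES analysis. Neither measures bias.

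The conclusion rests on two readings: that the interim analysis in SAP 5 is the first step of protocol 9.4, and that 9.2 sets a latest date without displacing 5 and 5.1. It would change if the unseen deviation or data review plans deferred PPS decisions until after the First Analysis, or if the primary tests were repeated at EOS on altered membership. Nothing in the protocol or SAP provides for either.

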9.2.1. Protocol Deviations Related to Study Conduct

A PD is any non-compliance with the clinical trial protocol, GCP, or protocol deviation guidelines requirements. The non-compliance may be either on the part of the participant, the site principal investigator (PI), the study site staff or the sponsor (or its delegate).

10. DEMOGRAPHIC AND OTHER BASELINE CHARACTERISTICS

Demographic data and other baseline characteristics will be presented for the ES and PPS. The following demographic and other baseline characteristics will be reported for this study:

- Age (years) – at the time of study intervention
- Age category (60-69, 70-79, ≥60, ≥65, ≥ 80 YOA)
- Sex
- Race (as per Clinical Data Interchange Standards Consortium [CDISC] categories)
- Ethnicity
- Country

Descriptive statistics (mean, median, standard deviation, and range) will be presented for continuous variables and frequency counts and percentages for categorical variables.

The number of participants enrolled in each country will be summarized by study intervention.

For web posting purposes, the demographic characteristics including age (based on EudraCT) and country will be presented for the enrolled set and screening set. In addition, the following age categories will be summarized: 18-64, 65-84, and >=85. If the summary of demographics meets the criteria for de-identification, as described in the relevant procedural document, a de-identified version will be produced.

No statistical testing will be carried out for demographic or other baseline characteristics.

11. GENERAL MEDICAL / VACCINATION HISTORY AND EXAMINATIONS

Medical / Vaccination History information will be summarized for the ES.

- Medical History will be coded using Medical Dictionary for Regulatory Activities (MedDRA) central coding dictionary, Version 25.1 or higher.
- Data captured on the “Medical History” page of the eCRF will be presented by MedDRA System Organ Class (SOC), High Level Terms (HLT) and Preferred Term (PT). Medical occurrences that begin before the start of study intervention but after obtaining informed consent will be recorded on the Medical History section of the eCRF, not the AE section.
- Medical history, classified by the MedDRA Primary SOC, HLT and PTs will be summarized for the ES. A listing of medical / vaccination history data will be provided.

12. PRIOR, CONCOMITANT AND Co-ADMINISTERED VACCINATIONS

Prior, concomitant, and co-administered vaccination will be coded with the current version of the World Health Organization Drug Dictionary (WHODD). Concomitant vaccinations during the 30-day follow-up period after each dose and overall will be summarized with exact 95% CI for the ES.

- Prior vaccinations are vaccinations per protocol given to participants prior to the dosing of study intervention and are recorded on the eCRF.
- Concomitant vaccinations are defined as any vaccine that the participant is receiving as of the time of enrolment or receives during the study (other than study interventions) as recorded on the “Concomitant Vaccination” page of the eCRF.

13. MEDICATIONS

The number and percentage of participants and doses using concomitant medication (any medication, any antipyretic and any antipyretic taken prophylactically, respectively) during the 7-day follow-up period (i.e., on the day of vaccination and 6 subsequent days), during the 30-day follow-up period (i.e., on the day of vaccination and 29

subsequent days) and during the 6-month follow-up period (i.e., up to EoS) will be summarized by study intervention group for each study intervention administration and overall will be summarized with exact 95% CIs for the ES. See [APPENDIX 2](#) for handling of partial dates for medications, in the case where it is not possible to define a medication as prior or concomitant, the medication will be classified by the worst case; i.e., concomitant.

- ‘Prior’ medications are medications which started prior to the dose of study intervention.
- ‘Concomitant’ medications are medications which started on or after the day of the administration of study intervention.

Further details are in Section 6.7 of the Protocol. Concomitant medications that start within the 7-days follow-up period and within the 30-days follow-up period post each dose will be presented in table summaries (Any, antipyretic action) for the ES and in listings for all medications. This summary will also be repeated for any concomitant medications that start from day of administration up to End of Study.

14. STUDY INTERVENTION EXPOSURE

Exposure to study intervention will be presented for the ES. The date and time of study intervention administration will be taken from the eCRF “Study intervention administration” forms (separate forms for PCV20 and RSVPreF3 OA investigational vaccine). For dosing instructions and route, refer to Table 5 of the Protocol.

